8.2 BASELINE EVALUATIONS

The following will be performed within 1 to 45 days prior to administration of study drug or surgery:

- History, physical
- Clinical examination with photograph of lesion if possible.
- Confirm tumor staging with CT or MRI scans of the head and neck and chest.
- Vital signs (i.e., temperature, heart rate, respiratory rate, blood pressure, body weight, and height)
- Hematology [(i.e., complete blood count (CBC) with automated differential]: WBC, RBC, HGB, HCT, platelet, MCV, MCH, MCHC, % neutrophils, absolute neutrophils, % monocytes, absolute monocytes, % eosinophils, absolute eosinophils, % basophils, absolute basophils, % lymphocyte, absolute lymphocyte, platelet confirmation (as clinically indicated), and differential confirmation (as clinically indicated)
- Chemistry (i.e., complete metabolic panel (CMP): chloride, CO₂, potassium, sodium, BUN, glucose, calcium, creatinine, total protein, albumin, total bilirubin, alkaline phosphatase, AST, ALT, A/G ratio, BUN/creatinine ratio, osmol (Calc), anion gap)
- Biopsy (diagnosis)
- HCG urine or serum for women of childbearing potential
- Performance status (ECOG): **Appendix D**
- Evaluate lesion size
- Quality of Life Questionnaire: **Appendix H**

8.3 DAY 0 INFUSION (ARM 2 – PDT WITH HPPH)

- Vital signs (i.e., temperature, heart rate, respiratory rate, blood pressure, and body weight)
- Correlative studies blood samples
- HPPH infusion
- Adverse events

8.4 DAY 1 TREATMENT

- Laser PDT with HPPH (Arm 2) or Surgery (Arm 1)
- Vital signs (i.e., temperature, heart rate, respiratory rate, blood pressure, and body weight)
- Optical spectroscopy (Arm 2)

- Normal tissue toxicity grade (Arm 2, **Appendix F**)

8.5 ABOUT 1 WEEK POST TREATMENT

- Clinical examination with photograph of lesion if possible
- Vital signs (i.e., temperature, heart rate, respiratory rate, blood pressure, and body weight)
- Correlative studies blood samples (for participants randomized to PDT only)
- Normal tissue toxicity grade (**Appendix F**)
- Adverse events

8.6 ABOUT 4 - 6 WEEKS POST TREATMENT

- Clinical examination with photograph of lesion if possible
- Vital signs (i.e., temperature, heart rate, respiratory rate, blood pressure, and body weight)
- Correlative studies blood samples (for participants randomized to PDT only)
- Normal tissue toxicity grade (for participants randomized to PDT only) (**Appendix F**)
- Adverse events

8.7 ABOUT 12 - 16 WEEKS POST TREATMENT

- Clinical examination with photograph of lesion if possible
- Vital signs (i.e., temperature, heart rate, respiratory rate, blood pressure, and body weight)
- Performance status (ECOG): **Appendix D**
- Response, clinical (for both arms)
- Response, pathological, biopsy for all participants.
- Quality of Life Questionnaire: **Appendix H**

8.8 POST-TREATMENT FOLLOW-UP EVALUATIONS

Post treatment follow-up evaluations will occur every 3 - 4 months in year 1, 3 - 6 months in year 2, per the NCCN guidelines.

- Clinical examination with photograph of lesion, if possible
- Vital signs (i.e., temperature, heart rate, respiratory rate, blood pressure, and body weight)
- Performance status (ECOG): **Appendix D**
- Response, clinical (at each follow-up and at 2 years)
- Response, pathological, biopsy, will be performed during routine visits, only if clinically indicated
- Confirm tumor staging with CT or MRI scans of the head and neck and chest, only if clinically indicated
- Quality of Life Questionnaire at 6, 12, 18, and 24 months: **Appendix H.**

8.9 SCHEDULE OF PROCEDURES AND OBSERVATIONS

The schedule of procedures and observations for this study is summarized in Table 2 and Table 3 below.

Table 2 Schedule of Procedures and Observations for Participants Randomized to PDT

	Baseline ¹	Day 0 Infusion	Day 1 Treatment	~1 Week Post Treatment	~4-6 Weeks Post Treatment	~12-16 Weeks Post Treatment	Follow-Up ²
History, Physical	X						
Clinical Exam (with lesion photograph if possible)	X			X	X	X	X
Confirm tumor staging with CT or MRI scans of the head and neck and chest	X						X ¹⁰
Vital Signs (i.e., temperature, heart rate, respiratory rate, blood pressure, body weight, and height) ³	X	X	X	X	X	X	X
Hematology ⁵	X						
Chemistry ⁶	X						
Blood Samples (if possible) for correlative studies (immune, photosensitizer & biomarker analyses ⁷		X		X	X		
Biopsy (diagnosis)	X						
HCG urine or serum for women of childbearing potential	X						
HPPH Infusion		X					
Optical spectroscopy			X				
Laser			X				
Normal Tissue Toxicity Grade			X	X	X		
Performance Status/ECOG	X					X	X
Response, Clinical (Evaluate Lesion Size)	X					X	X
Response, Pathological, Biopsy						X	X ⁸
Quality of Life Questions	X					X	X ⁹
Adverse Events		X		X	X		

	Baseline¹	Day 0 Infusion	Day 1 Treatment	~1 Week Post Treatment	~4-6 Weeks Post Treatment	~12-16 Weeks Post Treatment	Follow-Up²
1	Performed within 45 days prior to first dose of study drug.						
2	These follow-up to 2 years.						
3	Height collected at baseline only.						
4	Blood will be collected Pre-infusion.						
5	Hematology (CBC/automated differential: WBC, RBC, HGB, HCT, platelet, MCV, MCH, MCHC, %neutrophils, abs. neutrophils, %monocytes, abs. monocytes, %eosinophils, abs. eosinophils, %basophils, abs. basophils, %lymph T, abs. lymph T, platelet confirmation as clinically indicated, & differential confirmation as clinically indicated).						
6	Chemistry (i.e., complete metabolic panel (CMP): chloride, Co2, potassium, sodium, BUN, glucose, calcium, creatinine, total protein, albumin, total bilirubin, alkaline phosphatase, AST, ALT, A/G ratio, BUN/creatinine ratio, osmol (Calc), anion gap).						
7	Refer to Section 8.10 .						
8	Biopsy for response will be performed during routine visits, only if clinically indicated, and at 2 years.						
9	At 6, 12, 18 and 24 months.						
10	CT or MRI as clinically indicated.						

Table 3 Schedule of Procedures and Observations for Participants Randomized to Surgery

	Baseline ¹	Day 0	Day 1 Surgery	About 1 Week Post Surgery	About 4-6 W Post Surgery	About 12-16 W Post Surgery	Follow-Up ²
History, Physical	X						
Clinical Exam (with photograph of lesion if possible)	X			X	X	X	X
Confirm tumor staging with CT or MRI scans of the head and neck and chest	X						X ⁸
Vital Signs (i.e., temperature, heart rate, respiratory rate, blood pressure, body weight, and height) ³	X	X	X	X	X	X	X
Hematology ⁴	X						
Chemistry ⁵	X						
Biopsy (diagnosis)	X						
HCG urine or serum for women of childbearing potential	X						
Toxicity Grade				X	X		
Performance Status/ECOG	X					X	X
Response, Clinical (Evaluate Lesion Size)	X					X	X
Response, Pathological, Biopsy						X	X ⁶
Quality of Life Questionnaire	X					X	X ⁷
Adverse Events				X	X		

 1. Performed within 12 weeks prior to surgery. 2. These follow-up visits will be according to the NCCN guidelines for T1/T2 SCC of head and neck. 3. Height collected at baseline only. 4. Hematology (CBC/automated differential: WBC, RBC, HGB, HCT, platelet, MCV, MCH, MCHC, %neutrophils, abs. neutrophils, %monocytes, abs. monocytes, %eosinophils, abs. eosinophils, %basophils, abs. basophils, %lymph T, abs. lymph T, platelet confirmation as clinically indicated, & differential confirmation as clinically indicated). 5. Chemistry (i.e., complete metabolic panel (CMP): chloride, Co2, potassium, sodium, BUN, glucose, calcium, creatinine, total protein, albumin, total bilirubin, alkaline phosphatase, AST, ALT, A/G ratio, BUN/creatinine ratio, osmol (Calc), anion gap). 6. Biopsy for response will be performed during routine visits, only if clinically indicated, and at 2 years. 7. At 6, 12, 18 and 24 months. 8. CT or MRI as clinically indicated. 							

8.10 CORRELATIVE STUDIES SAMPLE COLLECTION AND PROCESSING

8.10.1 Immune Monitoring for Isolation and Storage of Immune Cells

This assay will be performed only for participants randomized to PDT with HPPH. Whole blood samples for immune monitoring for isolation and storage of immune cells will be collected via venipuncture using (1) 10 mL green-top heparinized collection tube. If possible, sample collection will be obtained at the following time points:

- Prior to infusion of HPPH on Day 0
- About 1 week after the infusion of HPPH
- About 4 – 6 weeks after the infusion of HPPH

Whole blood samples collected at RPCI will be sent at room temperature for processing the same day of collection.

Whole blood samples collected at participating sites will be shipped at room temperature on the day of collection Monday - Thursday. Do not ship specimens on Fridays or on day before a holiday. Samples should be clearly labelled with study #, patient initials, subject ID #, date of collection, source of material, (i.e. blood, serum) and sample time point (i.e. prior to infusion of HPPH, Day 0), Each subject should have their samples entered on a Network Specimen Requisition Form (Other) provided for you along with e-mail notification to [name]; [contact] and [contact]

The samples should be sent to:

Roswell Park Cancer Institute
Attn: Flow Cytometry – I 33616
[name]
[name]
[name] (8:30 am -5 pm)
[contact] and [contact]

Note: All investigator or analyzing research laboratories housing research samples need to maintain current **Temperature Logs** and study-specific **Sample Tracking and Shipping Logs**. The Principal Investigator/Laboratory Manager **must** ensure that the stated lab(s) have a process in place to document the receipt/processing/storage/shipping of study-related samples/specimens. This is required for both observational and interventional clinical studies collecting clinical samples.

8.10.2 Photosensitizer (HPPH) and Biomarker (Serum Alkaline DNase) Levels in Serum

This assay will be performed only for participants randomized to PDT with HPPH. Blood for determination of photosensitizer and biomarker levels will be collected via venipuncture using (1) 10 mL red-top collection tube. Whole blood should be allowed to clot and serum isolated via centrifugation. Caution should be used to prevent hemolysis. Sample collection will be obtained at the following time points:

- Prior to infusion of HPPH on Day 0
- About 1 week after the infusion of HPPH
- About 4 – 6 weeks after the infusion of HPPH

Whole blood samples collected at RPCI will be picked up at room temperature for processing in [name] laboratory the same day of collection.

Serum will be isolated per network site's SOP specific to their centrifuge. Isolated serum samples from participating sites will be frozen at site (-80C) and stored at site until notified by Network coordinator to batch ship all three-time points for each subject. Each patient will have a Network Specimen Requisition Form (Other) filled out and included in the shipment. Ship only on Monday-Thursday. Do not ship specimens on Fridays or on day before a holiday. Samples should be clearly labelled with study #, patient initials, subject ID #, date of collection, source of material, (i.e. blood, serum) and sample time point (i.e. prior to infusion of HPPH, Day 0), with e-mail notification:

Roswell Park Cancer Institute
Department of Cells Stress Biology
Attn: [name] – I 33616
[name]
[name]
[contact] or [contact]

[contact] and [contact]

Note: All investigator or analyzing research laboratories housing research samples need to maintain current **Temperature Logs** and study-specific **Sample Tracking and Shipping Logs**. The Principal Investigator/Laboratory Manager **must** ensure that the stated lab(s) have a process in place to document the receipt/processing/storage/shipping of study-related samples/specimens. This is required for both observational and interventional clinical studies collecting clinical samples.

8.10.3 Diffuse reflectance optical spectroscopy

This assay will be performed only for participants randomized to PDT with HPPH. Non-invasive reflectance spectroscopy will be performed to assess HPPH concentration, blood volume, and blood SO₂ within the lesion before and immediately after PDT. We will use the reflectance system marketed by Zenalux (Zenascope). This device has been approved by the IRB at RPCI for use in two ongoing clinical studies (I 235613 and I 239713). A short description of the system and the scientific rationale are provided in **Appendix B**.

The measurements will be done by placing the measurement probe (5 mm in diameter) in contact with the surface of the lesion for a few seconds. The probe will deliver low-intensity white light to the lesion and detect the reflected light. A total of 3-5 measurements will be taken from the center of each lesion, before and immediately after PDT. The data set will be identified by the participant's ID and stored on a secure laptop. The end of the probe will be disinfected after use in each participant by soaking it in Cidex for 15 minutes following the procedure described in **Appendix C**.

8.11 PATHOLOGY

At each site, the tumor biopsy will be sent to a surgical pathologist and processed for routine standard of care pathological examination. When tumor-biopsy morphology precludes objective evaluation by histopathology, ancillary immunohistochemical studies may be employed to determine the presence of tumor cells, by the pathologist. (If standard H&E cannot be used to evaluate the presence of tumor cells, the pathologist will use immunohistochemistry to evaluate the biopsy).

9 EFFICACY EVALUATIONS

9.1 OBJECTIVE TUMOR RESPONSE

Pathological tumor response will be evaluated by taking a 3-mm punch biopsy from the PDT treated or surgical area at 12-16 weeks after PDT or surgery. The participants from the PDT and surgery arms will be followed clinically up to 2 years. At the end of the follow up time, the treating physician will examine the clinical response and a photograph of the treatment site will be taken with paper ruler, to determine the reduction in the lesion size, according to RECIST v1.1. The study coordinator or nurse will take the photos. The treating physician will determine the lesion size with a caliper if photos can't be taken.

9.2 TARGET LESIONS

All identifiable lesions will be recorded with digital photography and clinical examination. The objective tumor response will be determined according to the following criteria per Recist v1.1:

- **Complete Response (CR):** Disappearance of all target lesions. Any lymph nodes must have a reduction in short axis to < 10 mm.

- **Partial Response (PR):** At least a 30% decrease in the sum of diameters of target lesions, taking as reference the baseline sum diameters. A biopsy will be taken from the suspected lesions for histological confirmation of squamous cell carcinoma.
- **Progressive Disease (PD):** At least a 20% increase in the sum of diameters of target lesions, taking as references the smallest sum on study (this includes the baseline sum if that is the smallest on study). In addition to the relative increase of 20%, the sum must also demonstrate an absolute increase of at least 5 mm. The appearance of one or more new lesions is also considered progression.
- **Stable Disease (SD):** Neither sufficient shrinkage to qualify for PR nor sufficient increase to qualify for PD, taking as reference the smallest sum diameters while on study, the response will be listed with stable disease. In this case, a biopsy will be taken from the suspected lesion for histological confirmation.

9.3 EVALUATION OF RESPONSE

Time point response assessments will be performed 12 - 16 weeks and 24 months after PDT. To determine time point response, refer to **Table 4** below.

Table 4 Time Point Response Criteria (+/- non-target disease)

Target Lesions	Non-Target Lesions	New Lesions	Overall Response
CR	CR	No	CR
CR	Non-CR/Non-PD	No	PR
CR	Not evaluated	No	PR
PR	Non-PD or not all evaluated	No	PR
SD	Non-PD or not all evaluated	No	SD
Not all evaluated	Non-PD	No	NE
PD	Any	Yes or No	PD
Any	PD	Yes or No	PD
Any	Any	Yes	PD

The best overall response is the best response recorded from the start of study treatment until follow-up is completed or the participant goes off study (the end of treatment taking into account any requirement for confirmation).

- **Symptomatic Deterioration:** Participants with global deterioration of health status requiring study withdrawal without objective evidence of disease progression at that time, and not related to study treatment or other medical conditions should be reported as progressive disease due to “symptomatic deterioration.” Every effort should be made to document objective progression even after discontinuation of treatment due to symptomatic deterioration. Symptomatic deterioration that may lead to study withdrawal includes, but is not limited to, symptoms such as:
 - Weight loss > 10% of body weight.

- Worsening of disease-related symptoms (e.g., worsening dyspnea, increasing pain/increasing requirement for narcotic analgesics).
- Decline in performance status of > 1 level on ECOG scale.

10 SAFETY EVALUATION

10.1 ADVERSE EVENTS

10.1.1 Definition

An adverse event or adverse experience (AE) is any untoward medical occurrence associated with the use of a drug in humans, whether or not considered drug related. Therefore, an AE can be **ANY** unfavorable and unintended sign (including an abnormal laboratory finding), symptom, or disease temporally associated with the use of a medicinal (investigational) product, whether or not considered related to the medicinal (investigational) product (attribution of ‘unrelated’, ‘unlikely’, ‘possible’, ‘probable’, or ‘definite’).

An AE is considered “unexpected” if it is not listed in the investigator brochure or is not listed at the specificity or severity that has been observed; or if an investigator brochure is not required or available, is not consistent with the risk information described in the general investigational plan in other study-related documents.

10.1.1.1 Diagnosis Versus Signs and Symptoms

If known, a diagnosis should be recorded on the CRF rather than individual signs and symptoms (e.g., record only liver failure or hepatitis rather than jaundice, asterixis, and elevated transaminases). However, if a constellation of signs and/or symptoms cannot be clinically characterized as a single diagnosis or syndrome at the time of reporting, each individual event should be recorded as an AE or SAE on the CRF. If a diagnosis is subsequently established, it should be reported as follow-up information.

10.1.1.2 Adverse Events Occurring Secondary to Other Events

In general, AEs occurring secondary to other events (e.g., cascade events or clinical sequelae) should be identified by their primary cause. For example, if severe diarrhea is known to have resulted in dehydration, it is sufficient to record only diarrhea as an AE or SAE on the CRF.

However, medically significant AEs occurring secondary to an initiating event that are separated in time should be recorded as independent events on the CRF. For example, if a severe gastrointestinal hemorrhage leads to renal failure, both events should be recorded separately on the CRF.

10.1.1.3 Abnormal Laboratory Values

Only clinically significant laboratory abnormalities that require active management will be recorded as AEs or SAEs on the CRF (e.g., abnormalities that require study drug dose modification, discontinuation of study treatment, more frequent follow-up assessments, further diagnostic investigation, etc.).

If the clinically significant laboratory abnormality is a sign of a disease or syndrome (e.g., alkaline phosphatase and bilirubin 5 x the upper limit of normal associated with cholecystitis), only the diagnosis (e.g., cholecystitis) needs to be recorded on the Adverse Event CRF.

If the clinically significant laboratory abnormality is not a sign of a disease or syndrome, the abnormality itself should be recorded as an AE or SAE on the CRF. If the laboratory abnormality can be characterized by a precise clinical term, the clinical term should be recorded as the AE or SAE. For example, an elevated serum potassium level of 7 mEq/L should be recorded as “hyperkalemia”.

Observations of the same clinically significant laboratory abnormality from visit to visit should not be repeatedly recorded as AEs or SAEs on the CRF, unless their severity, seriousness, or etiology changes.

10.1.1.4 Preexisting Medical Conditions (Baseline Conditions)

A preexisting medical condition should be recorded as an AE or SAE only if the frequency, severity, or character of the condition worsens during the study. When recording such events on an Adverse Event CRF, it is important to convey the concept that the preexisting condition has changed by including applicable descriptors (e.g., “more frequent headaches”).

10.1.2 Grading and Relationship to Drug

The descriptions and grading scales found in the CTEP Version 4 of the NCI Common Terminology Criteria for Adverse Events (CTCAE) will be utilized for AE reporting. CTEP Version 4 of the CTCAE is identified and located at:

http://ctep.cancer.gov/protocolDevelopment/electronic_applications/ctc.htm.

AEs not covered by specific terminology listed should be reported with common medical terminology and graded according to definitions provided in the CTCAE Version 4.

The relationship of event to study drug will be documented by the Investigator as follows:

- **Unrelated:** The event is clearly related to other factors such as the participant’s clinical state, other therapeutic interventions or concomitant drugs administered to the participant.
- **Unlikely:** The event is doubtfully related to investigational agent(s). The event was most likely related to other factors such as the participant’s clinical state, other therapeutic interventions, or concomitant drugs.
- **Possible:** The event follows a reasonable temporal sequence from the time of drug administration, but could have been produced by other factors such as the participant’s clinical state, other therapeutic interventions or concomitant drugs.
- **Probable:** The event follows a reasonable temporal sequence from the time of drug administration, and follows a known response pattern to the study drug. The event cannot be reasonably explained by other factors such as the participant’s clinical state, therapeutic interventions or concomitant drugs.

- **Definite:** The event follows a reasonable temporal sequence from the time of drug administration, follows a known response pattern to the study drug, cannot be reasonably explained by other factors such as the participant’s condition, therapeutic interventions or concomitant drugs; AND occurs immediately following study drug administration, improves upon stopping the drug, or reappears on re-exposure.

10.1.3 Reporting Routine Adverse Events

Table 5 Guidelines for Routine Adverse Event Reporting for Phase 2 Studies (Regardless of Expectedness)

Attribution	Grade 1	Grade 2	Grade 3	Grade 4
Unrelated			X	X
Unlikely			X	X
Possible	X	X	X	X
Probable	X	X	X	X
Definite	X	X	X	X

Routine AEs occurring between the start of intervention until 30 days after the last intervention or until the event has resolved, stabilized, death, or a new treatment is started, whichever comes first, will be reported. New information will be reported after it is received.

Photolitec, LLC. Buffalo, NY will be receiving copies of all the reports (de-identified).

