
Study Procedures
	
Disease Evaluation: Baseline and as per the NCCN guidelines for T1/T2 SCC of the head and neck. Quality of Life Questionnaire: Baseline, post treatment at 12 - 16 weeks and 6, 12, 18, and 24 months. Hematology: Baseline. Chemistry: Baseline. Performance Status: Baseline, post treatment at 12 - 16 weeks, and at follow-up visits. Clinical Examination: Baseline and post treatment at 1 week, 4 - 6 weeks, 12 - 16 weeks. We will follow the subjects according to the NCCN guidelines for patients with T1/T2 SCC, i.e. every 3 – 4 months (year 1), 3 – 6 months (year 2). Vital Signs: Baseline, Day 0, post treatment at 1 week, 4 - 6 weeks, 12 - 16 weeks, and at follow-up visits. HPPH Infusion: Day 0 Blood Samples: Day 0, 7, and 4-6 weeks Optical Spectroscopy: Day 1 Laser: Day 1 Adverse Events: From administration of study drug or surgery until 30 days after receiving study drug or surgery.

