4.3 MANAGEMENT OF THE NECK AND SALVAGE SURGERY

The management of the neck will be according to standard of care, at the discretion of the treating surgeon. If the participant, based on the pathology of the neck dissection or primary oral cancer resection, has perineural invasion, extracapsular spread, or requires additional therapies including radiation or chemotherapy, they will be dropped from the study and replaced with another participant.

Participants will receive standard curative therapy 6 weeks after failing to respond to PDT with HPPH. All the participants who will have disease progression, local recurrence, or partial or no response (PR, NR) following the PDT with HPPH will be considered treatment failures. The determination will be performed during the study visits, and based on clinical exam and pathology, if clinical exam is unclear.

The surgeon will provide a surgical plan for every patient, including those randomized to PDT. If the patient requires salvage surgery post-PDT, the surgeon will compare the salvage surgery specimen diameter to the diameter of the spot size used for PDT. This data will be used to demonstrate whether PDT affects the surgical plan.

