10.2.2 Reporting Serious Adverse Events

All new SAEs occurring from the date of the HPPH study drug infusion until 30 days after the HPPH Drug infusion, or PDT light treatment, will be reported to the IRB, in accordance to RPCI guidelines. The RPCI SAE Source Form is to be completed with all available information, including a brief narrative describing the SAE and any other relevant information.

SAEs occurring after the 30 day follow up period that the investigator determines to be possibly, probably or definitely related to the study intervention should be reported.

SAE's identified as an Unanticipated Problem by the Investigator must be reported. Please refer to **Section 10.5** for details on reporting Unanticipated Problems.

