12.2 SAMPLE SIZE DETERMINATION

In the proposed randomized trial, participants will be randomized to the treatment arms using a stratified block randomization scheme, with blocking stratified by clinical site (RPCI, and two other participating sites). Participants will be included in data analyses according to their randomized treatment assignment irrespective of the treatment actually received (intent-to-treat). Exceptions would include those who withdraw their consent to use any of their data prior to receiving any study medication. Initiation of study treatment will take place as soon as possible following randomization. No method of imputation will be used for missing data. All available data from participants who fail to complete this study will be included in all safety summaries.

The safety of the interventions will be assessed through the evaluation of Grade 3 or higher toxicities deemed possibly related to treatment. Both efficacy (e.g., tumor response) and toxicity rates will be estimated using simple relative frequencies. The corresponding 95% confidence intervals for the estimated probabilities will be computed using the method proposed in Clopper and Pearson (1934).

The design for this study is based on a test for non-inferiority of PDT compared to standard of care with regards to tumor response at 24 months post-procedure. Justification for use of a non-inferiority trial is that PDT may be viewed as a potential replacement for standard of care if it is established as less toxic than the standard of care yet still providing acceptable efficacy. Let π_{SOC}

and π_{PDT} are the probabilities of tumor response in the standard of care and PDT groups, respectively. The hypotheses corresponding to the proposed non-inferiority trial are

$$H_0 : \pi_{PDT} \leq \pi_{SOC} - \Delta,$$
$$H_a : \pi_{PDT} > \pi_{SOC} - \Delta,$$

where Δ is the non-inferiority margin. Specifically, we will be using the approach of Farrington-Manning to test our hypothesis via a score based test.⁵³

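### Routine adverse event reporting ends before any salvage treatment, so the planned Grade 3 or higher toxicity rates cannot show whether starting with PDT is less toxic than surgery

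*Combined protocol and SAP*

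**What the plan says.** **AE window.** Section 10.1.3 covers "Routine AEs occurring between the start of intervention until 30 days after the last intervention", or until the event settles, the participant dies, "or a new treatment is started, whichever comes first". The synopsis (Study Procedures) gives "From administration of study drug or surgery until 30 days after receiving study drug or surgery" and has no new-treatment cut-off. In Tables 2 and 3 (section 8.9) the last AE assessment in either arm is at about 4-6 weeks.

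**SAE window.** Section 10.2.2 runs from the HPPH infusion "until 30 days after the HPPH Drug infusion, or PDT light treatment", with no starting point for surgery. After that it asks for "SAEs occurring after the 30 day follow up period that the investigator determines to be possibly, probably or definitely related to the study intervention". Appendix A, item 8, has network sites report every SAE whatever its relation to the drug, and states no time limit.

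**Salvage.** Section 4.3: "Participants will receive standard curative therapy 6 weeks after failing to respond to PDT with HPPH". Section 1.2 puts local recurrence after first surgery at up to 20%, mostly managed by operating again.

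**Analysis.** Section 12.2: "Participants will be included in data analyses according to their randomized treatment assignment irrespective of the treatment actually received". The safety measure there is the proportion with Grade 3 or higher toxicity judged possibly related to treatment. Section 10.1.2 classes events clearly due to another therapeutic intervention as unrelated. Section 12.2 and the synopsis justify a non-inferiority design on the ground that PDT could replace surgery if shown to be less toxic, and section 12.1 relies on surgery being able to rescue PDT failures.

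**The concern.** The plan argues for a sequence: PDT first, with surgery held back for failures. Its toxicity data describe only the first step of that sequence. Operative toxicity is meant to be recorded when surgery is the assigned treatment, but not when surgery follows a PDT failure. Nor is it recorded when a recurrence after assigned surgery needs a second operation.

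Because both arms lose their salvage events, the effect on the comparison depends on how many salvages each arm has. If PDT fails more often, more events go missing from the PDT arm, and its toxicity looks better because its efficacy is worse. The statement at stake is the one the design rests on: that PDT, with surgery in reserve, is the less toxic choice.

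**Working it through.** The plan states no toxicity figure to reproduce. Its one design figure built on the same response rates and margin is the power of about 80% in section 12.2. The Farrington-Manning test with 57 per arm, 85% in both and a 20-point margin gives 81.5% at one-sided 0.025 (89.1% at one-sided 0.05). The inputs below are therefore the ones the plan used.

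**1. Does salvage fall outside the window?**
- The earliest reading of section 4.3 counts the 6 weeks from PDT itself: 6 x 7 = 42 days, which is 42 - 30 = 12 days past the 30-day limit. Counted from a later finding of failure, the gap is longer. The first scheduled response assessment is at 12-16 weeks (section 9.3).
- If salvage began sooner, the new-treatment clause in section 10.1.3 would close reporting anyway.
- Re-treatment of a recurrence in the surgery arm meets the same two limits.
- No section schedules AE collection after salvage in either arm.

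**2. Could reported SAEs restore the missing events?** Late SAEs under section 10.2.2 must be related to the study intervention. Appendix A is broader, but it describes reports to the local IRB, the network monitor and the manufacturer. An event clearly due to the salvage operation is unrelated under section 10.1.2, so it would not count as toxicity possibly related to treatment under section 12.2.

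**3. How many salvages go uncounted?** Inputs: 57 per arm; 85% response in both arms and a 20-point margin (section 12.2); 82% complete response with HPPH-PDT in the earlier study (section 12.1). Expected failures = 57 x (1 - response), assuming every failure is salvaged. The net is the PDT count minus the surgery count.

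| PDT / surgery response | PDT failures | Surgery failures | Net |
|---|---|---|---|
| 85% / 85% | 57 x 0.15 = 8.55 | 57 x 0.15 = 8.55 | 0 |
| 82% / 85% | 57 x 0.18 = 10.26 | 8.55 | 1.71 |
| 65% / 85% (margin) | 57 x 0.35 = 19.95 | 8.55 | 11.4 |

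**4. What does that do to the rates?** The documents give no toxicity rate for salvage. Assume that a proportion s = 10% to 40% of salvaged patients have a Grade 3 or higher event, the same in both arms. Net uncounted patients = net salvages x s, and points of the arm rate = that number / 57.
- 85% / 85%: zero.
- 82% / 85%: 1.71 x 0.10 = 0.17 to 1.71 x 0.40 = 0.68 patients, or 0.3 to 1.2 points.
- 65% / 85%: 11.4 x 0.10 = 1.14 to 11.4 x 0.40 = 4.56 patients, or 2.0 to 8.0 points.

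**5. Limits of these figures.** They assume that no salvaged patient already counts for index-treatment toxicity. Such overlap, if similar in the two arms, makes the net smaller, so 2 to 8 points is an upper value on that basis. If overlap were much commoner in the surgery arm, the net could be larger. It could not exceed the PDT arm's own gross omission, 0.35 x 0.10 = 3.5 to 0.35 x 0.40 = 14 points.

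**The case against.** A reader might infer that salvage toxicity is never recorded. The documents do not support that. Late related SAEs remain reportable (section 10.2.2), network sites report all SAEs (Appendix A), and quality of life runs to 24 months with analysis as randomised, so it can reflect salvage morbidity unless the participant has been withdrawn (section 7.4 lists progression as a reason). The need for salvage also feeds the stopping rule in section 10.6. The word surgery in the synopsis window might even be read to include a salvage operation, although section 10.1.3 and Table 2 do not bear that out. Section 12.2 puts all available data on non-completers into the safety summaries, but that does not create data nobody collects. What stands is that the gap lies in routine AEs and in the planned rates, not in all reporting.

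A reader might also infer an established bias towards PDT, sized from PDT failures alone. For example, the cited mTHPC result of 85% response kept by 85% at one year gives 0.85 x 0.85 = 72%, or 57 x 0.2775 = 15.8 uncounted salvages. That is a different photosensitizer and a one-arm count. The surgery arm loses its recurrences too: 8.55 at 15%, or 57 x 0.20 = 11.4 at 20%. Other gaps point the opposite way. Late morbidity of primary surgery is cut off at 30 days, the SAE window has no surgical starting point, participants with adverse surgical pathology are dropped and replaced (section 4.3), and the synopsis names only PDT participants as evaluable for toxicity, though section 12.4 is broader. The net direction of the whole comparison is therefore not settled.

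Finally, index-treatment toxicity is a legitimate target for a phase II trial. The objective is to assess toxicity, no toxicity test is specified, and section 2 frames the hypothesis around the initial treatment. This also stands, and it is a reason to keep that figure. It does not answer the plan's own argument, which uses salvage to justify accepting PDT failures and lower toxicity to justify the design.

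**Conclusion.** The point holds in a limited form. Routine AE reporting ends before treatment for failure or recurrence, so that toxicity is missing from the planned Grade 3 or higher rates in both arms, and the remaining SAE routes are not linked to the analysis. With equal failure the omission cancels, at about 8.6 salvages per arm. It favours PDT to the extent that PDT fails more often, reaching a net 11.4 salvages and about 1 to 5 patients (2 to 8 points) at the limit the margin allows. That size rests on an assumed 10-40% toxicity rate that is equal in both arms, on every failure being salvaged (section 4.1.2 says only that standard therapy is offered, at the physician's discretion), and on similar overlap with index-treatment toxicity. The index-treatment comparison remains valid for what it measures, but by itself it cannot support the statement that PDT first is less toxic than surgery. The change is cheap and should be made.

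**What to change.** - **Section 10.1.3, synopsis, Tables 2 and 3:** in both arms, collect Grade 3 or higher AEs from the start of any treatment for failure or recurrence until 30 days after it. Include participants taken off study for progression under section 7.4 who have not withdrawn consent.
- **Section 10.2.2:** reconcile the SAE window, now tied only to HPPH or light, with the surgery arm, with the collection period above and with Appendix A.
- **Sections 12.2 and 12.4:** report Grade 3 or higher toxicity by randomised arm for (a) index treatment and (b) index plus salvage, counting in (b) events related to the salvage procedure. Align the synopsis safety paragraph with section 12.4 so that both arms are evaluable.

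The cost is extra AE forms for about 9 to 20 PDT-arm participants (85% down to 65% response) and for surgery-arm recurrences, all in people the plan already intends to follow to 24 months. The PDT toxicity figure may turn out less favourable. No treatment or visit decision changes, and the index-treatment comparison is kept.
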